All randomizations are conducted intra-hospital (i.e., no cluster randomization), to avoid the confounding effect of practice variation. Randomization will be conducted in blocks of 10 to allow better distribution between groups at each interim analysis. It will be done by the Data Coordinating Center (DCC) and automated in an web-based REDCap data collection instrument. Upon confirmed eligibility and consent, the REDCap will reveal the group assignment to institution's pharmacy, which will then release the drug if the patient is assigned to the intervention group (Group tPA50, Group tPA50+drip). Time zero is assigned as the time of randomization. We anticipate that each of the five centers will enroll 8-12 patients.

The figure below illustrates the initial planned sequential, stepped-wedge design and the proposed new design after the adaptations driven by the first interim analysis. Study will continue during the interim analyses, unless a safety issue occurs.

INITIAL DESIGN

NEW DESIGN AFTER 1st INTERIM ANALYSIS

Re-bolusing of tPA, at the same dose, is permitted in the tPA50 intervention group in those patients who show an initial transient response (>20% improvement of PaO₂/FiO₂ over pre-infusion of alteplase at any of the measurements at 2, 6, 12 or 18 hours, but <50% improvement of PaO₂/FiO₂ at 24 hours after randomization); the repeat dose will be given between 24 and 36 hours after the initial tPA administration.

The same EXCLUSION criteria apply to the second tPA (alteplase) bolus. The heparin drip should be stopped two hours before the second tPA (alteplase) and re-started after the second alteplase infusion ends, at the same dose as before the second alteplase.

Other modifications of the dosing are as follows:

- Fibrinogen monitoring:** For all tPA administration groups, fibrinogen levels will be measured before and after tPA IV bolus, 6 hours after the start of the infusion, then every 6 hours for first 24 hours, and once a day for 6 days following treatment intervention in all the groups (see detailed lab testing schedule below). **If fibrinogen levels fall below 300 mg/dL, the second bolus of tPA (alteplase) is NOT indicated.**

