- 2) If at the end of the second intervention deployment (total of 20 patients randomized), the primary outcome improves (PaO₂/FiO₂ ratio at 48 hours) by $\geq 20\%$, or the secondary outcomes PaO₂/FiO₂ ratio at 24 hours improves $\geq 20\%$, or dead space decreases by 15%, or ICU- or ventilator-free days continue to exhibit a positive response (at least 2 days difference), we will modify the mode of administration of the second dose of tPA as follows: following the 50mg tPA bolus, we will initiate a drip of 2 mg/hr tPA over the ensuing 24 hours (total 48 mg infusion) accompanied by an infusion of 500 U/hour heparin during the tPA drip. After this, heparin dose will be increased slowly to maintain a PTT between 60 and 80 sec, titrated per attending's discretion. Interim analyses will be conducted as planned above, and submitted expeditiously to the DSMB, IRB and FDA for approval, yet enrollment will continue while these agencies deliberate and their feedback is received.

See above for the rationale for the tPA50+drip.

Statistical analysis (see attached Statistical Analysis Plan):

All analyses will be conducted initially as an intent-to-treat (patients are analyzed in the group they were randomized to), followed by an as-treated analysis. We will use linear mixed models (continuous outcomes, appropriate transformations if residuals normality departure is detected) or generalized estimating equations (categorical outcomes) to account for intra-hospital cluster effects and repeated measures, with FINAL (OVERALL) significance at $p < 0.05$ (two-tailed tests). If the groups are not comparable, we will compare relative (as opposed to absolute improvement over baseline (with patients as their own controls) to minimize the effect of baseline disparities. In addition, as the sample permits, we will adjust for confounders using a single propensity score adjustor in an inverse probability weighting approach. In addition, we will compare the "dose" of the intervention (i.e., how much of the treatment the patient received) as the effect of interest. The pre-planned final comparisons include within group (improvement over baseline) and between groups, all two-tailed with significance declared according to the alpha defined above by the Pocock spending method.

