Retroperitoneal bleeding		Clinical exam pre, during and immediately post alteplase infusion; every 6 hours post alteplase infusion up to 24 hours; at least every 24 hours after alteplase infusion during heparin infusion or more frequently if any abnormality detected. Endoscopic exam per attending's discretion.	Hemoglobin reduction $>3\text{g/dL}$ within 24 hours of infusion of study drug infusion or requiring RBC transfusion
Tube thoracotomy	Clinical exam and Hgb	Clinical exam pre, during and immediately post alteplase infusion; every 6 hours post alteplase infusion up to 24 hours; at least every 24 hours after alteplase infusion during heparin infusion or more frequently if any abnormality detected.	Hemoglobin reduction $>3\text{g/dL}$ within 24 hours of infusion of study drug infusion or requiring RBC transfusion
Any of the below listed exclusion criteria developing during or up to 3 hours after alteplase or heparin infusion. **	Clinical exam and laboratory		Any of listed exclusion criteria developing during or up to 3 hours after alteplase or heparin infusion.

*criteria or attending's decision

** criteria: Acute myocardial infarction; Acute Renal failure requiring dialysis; Liver failure (escalating liver failure with total Bilirubin $> 3 \text{ mg/dL}$); Cardiac tamponade; Bacterial endocarditis; Severe

uncontrolled hypertension defined as SBP>185mmHg or DBP>110mmHg; Seizure; Placement on ECMO; Major surgery required; Requirement of lumbar puncture; INR > 1.7; Platelet count < 100 x 10⁹/L or history of HIT.

Reporting of adverse events:

Any adverse event will be immediately and properly reported to IRB and DSMB, FDA and funding agency for discussion and feedback per regulatory guidelines.

Major Milestones, Tasks, Timelines and Deliverables

	Done	Essential For Initiation	Week From Secured Funding								Week 16
			1	2	3	4	5	6	7	8	
PREPARATION											
Establish Core Research Team	X										
Review existing literature	X										
Implement Protocol	X										
Finalize Study Protocol	X										
Finalize Statistical Analysis Plan	X										
Finalize Case Report Form	X										
Enlist Collaborating Institutions	X										
Submit Protocol for Funding	X										
Review Protocol Data	X										
REGULATORY OVERSIGHT											
FDA IND		X									
IRB Approval		X									
ClinicalTrial.gov Registration		X									
FUNDING SECURED											
Secure DSMB			X								
Hire Research Team	X										

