Hemoptysis	Clinical exam	Clinical exam pre, during and immediately post alteplase infusion; every 6 hours post alteplase infusion up to 24 hours; at least every 24 hours after alteplase infusion during heparin infusion or more frequently if any abnormality detected. Endoscopic exam per attending's discretion.	Persistent hemoptysis for $\geq 4$ hours or compromising airway
Hematuria	Clinical exam	Clinical exam pre, during and immediately post alteplase infusion; every 6 hours post alteplase infusion up to 24 hours; at least every 24 hours after alteplase infusion during heparin infusion or more frequently if any abnormality detected. Endoscopic exam per attending's discretion.	Persistent hematuria for $\geq 4$ hours or urinary obstruction
Retroperitoneal bleeding		Clinical exam pre, during and immediately post alteplase infusion; every 6 hours post alteplase infusion up to 24 hours; at least every 24 hours after alteplase infusion during heparin infusion or more frequently if any abnormality detected. Endoscopic exam per attending's discretion.	Hemoglobin reduction $>3\text{g/dL}$ within 24 hours of infusion of study drug infusion or requiring RBC transfusion
Tube thoracotomy	Clinical exam and Hgb	Clinical exam pre, during and immediately post alteplase infusion; every 6 hours post alteplase infusion up to 24 hours; at least every 24 hours after alteplase infusion during	Hemoglobin reduction $>3\text{g/dL}$ within 24 hours of infusion of study drug infusion or requiring RBC transfusion

Serious Adverse Events	Method for safety check	Safety check frequency	Cessation rule *
		heparin infusion or more frequently if any abnormality detected.	
Any of the below listed exclusion criteria developing during or up to 3 hours after alteplase or heparin infusion, except for fibrinogen, for which we will set cessation cutoff at 300mg/dL **	Clinical exam and laboratory		Any of listed exclusion criteria developing during or up to 3 hours after alteplase or heparin infusion, except for fibrinogen, for which we will set cessation cutoff at 300mg/dL

\*criteria or attending's decision

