\*\* criteria: Acute myocardial infarction; Acute Renal failure (escalating renal failure with creatinine >3 times baseline); Liver failure (escalating liver failure with ALT> 3 times baseline); Cardiac tamponade; Bacterial endocarditis; Severe uncontrolled hypertension defined as SBP>185mmHg or DBP>110mmHg; Seizure; Placement on ECMO; Major surgery required; Requirement of lumbar puncture; INR > 1.7; Platelet count < 100 x 10^9/L or history of HITT; Fibrinogen < 300mg/dL

**8. Dataset availability:** a de-identified dataset will be made available to other investigators who may submit proposals to the PI for additional analyses or validation.

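### For fibrinogen below 300 mg/dL the SAP stops study drug and the Protocol of the same date does not, so a running 24-hour tPA drip falls under two different rules

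*SAP*

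**What the plan says.** **SAP, Section 7 (Safety check assessments: methods and timing).** The last row of the cessation table stops drug for listed exclusion criteria that develop while alteplase or heparin is running or within 3 hours of it, "except for fibrinogen, for which we will set cessation cutoff at 300mg/dL". The footnote that defines the list ends with "history of HITT; Fibrinogen < 300mg/dL".

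**Protocol, same table and footnote.** The row has the same time window but no fibrinogen clause. The footnote list ends at "INR > 1.7; Platelet count < 100 x 10⁹/L or history of HIT". A second footnote lets drug be stopped on "criteria or attending's decision".

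**Protocol, Fibrinogen monitoring.** Testing covers every tPA arm: "For all tPA administration groups, fibrinogen levels will be measured before and after tPA IV bolus", then at hour 6 and six-hourly to hour 24. One action follows from a low result: "If fibrinogen levels fall below 300 mg/dL, the second bolus of tPA (alteplase) is NOT indicated".

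**Protocol, re-bolus rule and amendment of 11/5/2020.** "Re-bolusing of tPA, at the same dose, is permitted in the tPA50 intervention group". The second branch of the amendment introduces the drip with the words "we will modify the mode of administration of the second dose of tPA as follows".

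**Both documents, enrolment.** Fibrinogen below 300 mg/dL is an exclusion criterion in each.

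**The concern.** Neither document supersedes the other by date, and they give different instructions for the same laboratory result. The drip delivers 2 mg/hr for 24 hours, and fibrinogen is measured while it runs. A patient whose value first falls below 300 mg/dL during the drip has the thrombolytic stopped under the SAP. Under the Protocol it continues unless the attending intervenes or another stop applies. Both documents already regard that value as too low to start tPA, so this is a bleeding-safety matter.

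The SAP describes safety monitoring as following the protocol, so bedside dosing would ordinarily be taken from the Protocol, which is the document without the stop.

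The analysis is touched less. Intention-to-treat assignment does not change. Received dose, however, enters the dose comparison (SAP 6.4) and the received-dose subgroup (SAP 6.5), and all analyses, safety included, are repeated as-treated (SAP 4.3).

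**Working it through.** **Step 1: the cessation lists side by side.**

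| Criterion | Protocol footnote | SAP Section 7 |
|---|---|---|
| Fibrinogen | not listed | below 300 mg/dL |
| Liver | total bilirubin > 3 mg/dL | ALT > 3 times baseline |
| Renal | dialysis required | creatinine > 3 times baseline |

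Three criteria differ. INR, platelets and the remaining entries agree in substance.

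**Step 2: does another Protocol rule supply the fibrinogen stop?** The value is used in two other places. As an exclusion it is applied at enrolment. As a treatment rule it bars a second bolus, and re-bolusing is described for the tPA50 group. Because the amendment presents the drip as a changed form of the second dose, the bar could be read as preventing the drip from being started after a low post-bolus value. It could equally be read as not reaching the drip at all. On neither reading does it stop a drip that is already running.

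**Step 3: tPA dose on which the documents differ.**

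Inputs: drip 2 mg/hr for 24 hours, 48 mg in total (Protocol, Group tPA50 plus drip); bolus over 2 hours, 50 mg capped at 0.9 mg/kg; fibrinogen at hours 6, 12, 18 and 24 (Protocol, Laboratory Measurements). Assumed timeline: bolus hours 0–2, drip hours 2–26, post-bolus test at hour 2.

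Drip remaining at hour h = 48 − 2 × (h − 2) mg. The full 50 mg bolus is allowed from 50 / 0.9 = 55.6 kg, giving a total of 50 + 48 = 98 mg. A 50 kg patient receives 0.9 × 50 = 45 mg, a total of 93 mg.

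| First low value | Remaining (mg) | Share of 98 mg | Share of 93 mg |
|---|---|---|---|
| Hour 6 | 48 − 8 = 40 | 41% | 43% |
| Hour 12 | 48 − 20 = 28 | 29% | 30% |
| Hour 18 | 48 − 32 = 16 | 16% | 17% |
| Hour 24 | 48 − 44 = 4 | 4% | 4% |

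These are upper limits. Each hour between sampling and stopping reduces the difference by 2 mg, and the attending may stop the drip under the Protocol as well. For a low value at the post-bolus test, the difference is 48 mg if the second-bolus bar does not cover the drip and 0 mg if it does.

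**Step 4: patients exposed.** SAP 3.1 plans the drip arm after the first 20 patients, up to 50. At 1:1 allocation, (50 − 20) / 2 = 15 patients. If the 48-hour outcome improves by at least 50% at the second look, the bolus regimen continues and the number is 0.

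**Step 5: heparin.** The SAP window also covers heparin, which runs for up to 7 days (Protocol, Heparin dosing), with fibrinogen measured daily after hour 24. On its face the SAP would stop heparin for a low value in that period, and the Protocol would not. This difference exists in the tPA50 arm even if the drip is never used.

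**The case against.** A reader might infer that the Protocol has no rule at all for stopping a running drip. The documents do not support that. The Protocol's cessation table stops drug for cardio-pulmonary arrest, allergic reaction, neurological decline, a fall of 30% or more in PaO₂/FiO₂ and defined bleeding, and its footnote adds INR, platelets and other events. The gap is specific to low fibrinogen.

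A second objection is that the documents show a conflict without showing which side is right. There are signs that the SAP list is the older text: its renal stop uses creatinine while its own renal exclusion uses dialysis, and its fibrinogen exception is redundant because 300 mg/dL is already the exclusion value. The Protocol's bilirubin criterion, by contrast, is consistent across its exclusions, laboratory schedule and cessation list. The Protocol may have meant low fibrinogen to bar only further boluses, and a value too low to start tPA does not by itself settle when to stop it. This stands in part. It is a reason to leave the liver and renal choices open. It does not let two different fibrinogen rules coexist, and adopting the tPA stop carries across something the SAP already states.

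The third objection stands in full: adding fibrinogen to the Protocol row without qualification would, on its face, also stop heparin for up to 7 days. The Protocol gives heparin to prevent rebound thrombosis and regards it as standard care, so its scope must be decided separately.

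**Conclusion.** The conflict is established from the text and should be corrected before the drip is used. The SAP makes fibrinogen below 300 mg/dL a reason to stop study drug. The Protocol does not, and for that result only the attending's decision would end a running drip. The size is at most 40, 28, 16 or 4 mg of tPA per affected patient, depending on when the value first falls, in about 15 patients or in none. This rests on the assumed timeline, 1:1 allocation, and immediate reporting and stopping.

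The documents give no frequency for fibrinogen below 300 mg/dL, so no expected number of affected patients or bleeds can be derived. Nor do they show that the as-treated or dose results would shift by any particular amount. The liver and renal cessation criteria also conflict, and which version is preferable is a clinical question.

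**What to change.** Wrong as written; three changes are needed.

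1. **Protocol, Fibrinogen monitoring.** Replace the second-bolus sentence with a rule that covers the drip, for example: *When fibrinogen is under 300 mg/dL, give no second bolus; do not start the tPA drip; stop it if it is running.*
2. **Protocol cessation list.** Add the same tPA stop. State in both the Protocol table and SAP Section 7 whether it also applies to heparin. That choice belongs to the clinical team and the DSMB.
3. **One list.** Carry an identical cessation list in the Protocol and the SAP, with the clinical team choosing the liver and renal criteria. The laboratory schedule has total bilirubin before treatment only and neither ALT nor creatinine. Whichever criteria are chosen, the text should say whether they use routine ICU values or a scheduled test.

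**Cost.** Both documents must be amended and refiled; SAP 6.5 already expects a new version to go to the IRBs, DSMB, funder and FDA when subgroups are added. Some patients will receive less tPA. The fibrinogen stop needs no new test, and the Protocol's adaptive plan already foresees coagulation variables as cessation rules.

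**Housekeeping only.** Align the exclusion lists on prisoner status, which only the Protocol includes, and delete the SAP's redundant fibrinogen exception.
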